- e After the study site is notified of end of study decision, an EOS Visit should be scheduled as soon as possible (but within 4 weeks at the latest).
- f For all participants still on treatment with study drug at the EOS Visit, the post-treatment (PT) telephone call (☎) has to be performed 30 days +5 days after the last intake of study drug.
- g For vital sign collection, please adhere to instructions in Section [8.2.2](#).
- h If BNP, NT-proBNP values (related to inclusion criteria) are not available in medical records, use values assessed by local laboratory.
- i Creatinine will be used to calculate eGFR using CKD-EPI ([Horio et al. 2010](#), [Levey et al. 2009](#))
- j If local laboratory data for potassium and eGFR are available within the last 24 hours, these may be used instead. This also applies when screening and baseline visits are not combined.
- k Study participants may have their local laboratory assessments taken up to 3 days prior to the study visit.
- l Female participants of childbearing potential must have a negative serum or urine pregnancy test at screening and baseline. Further serum or urine pregnancy tests should be performed in participants of childbearing potential as required by national/institutional regulations (e.g. at every visit). At any time during study participation, additional pregnancy testing should be performed upon suspicion of pregnancy.
- m All procedures at Visit 1 are to be performed prior to randomization.
- n One trough sample is to be collected at steady state before study intervention intake at Visit 3 (if not possible e.g. because study intervention was taken at home before the visit, the trough sample collection can be postponed to Visit 4 or 5); study intervention is to be administered at the study site at this visit.
- o Sample to be taken during the visit 1.5-10 hours after study intervention intake at home.
- p The procedures/assessments to be performed at the PD Visit are listed in the main SoA ([Figure 1-1](#)). After completing the PD Visit, all subsequent visits are to be performed according to the Premature Discontinuation SoA ([Figure 1-2](#)). Any visits performed prior to the PD Visit do not need to be repeated (e.g. if PD is at Visit 5, there is no need to repeat previous visits).
- q Questionnaires are to be completed by the participants before conducting any study procedure. See also Sections [8.1.1](#), [8.1.2](#) and [8.1.3](#) for details.
- r Only if applicable.

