**Medical Conditions**

1. eGFR <25 mL/min/1.73 m^2 at either screening or randomization visit.  
NOTE: one reassessment of eGFR is allowed at the screening and randomization visit, respectively
2. Serum/plasma potassium >5.0 mmol/L at either screening or randomization visit.  
NOTE: one reassessment of potassium is allowed at the screening and randomization visit, respectively
3. Acute inflammatory heart disease, e.g. acute myocarditis, within 90 days prior to randomization
4. Myocardial infarction or any event which could have reduced the ejection fraction within 90 days prior to randomization
5. Coronary artery bypass graft surgery in the 90 days prior to randomization
6. Percutaneous coronary intervention in the 30 days prior to randomization
7. Stroke or transient ischemic cerebral attack within 90 days prior to randomization
8. Probable alternative cause of participants' HF symptoms that in the opinion of the investigator primarily accounts for patient's dyspnea such as significant pulmonary disease, anemia or obesity. Specifically, patients with the below are excluded:
  - Severe pulmonary disease requiring home oxygen, or chronic oral steroid therapy
  - History of primary pulmonary arterial hypertension
  - Hemoglobin <10 g/dl\*
  - Valvular heart disease considered by the investigator to be clinically significant
  - Body mass index (BMI) >50 kg/m^2 at screening
9. Systolic blood pressure (SBP) ≥160 mmHg if not on treatment with ≥3 blood pressure lowering medications or ≥180 mmHg irrespective of treatments on 2 consecutive measurements at least 2-minute apart, at screening or at randomization

10. Life-threatening or uncontrolled arrhythmias at screening and/or randomization including but not limited to sustained ventricular tachycardia and atrial fibrillation, or atrial flutter with resting ventricular rate >110 bpm
11. Symptomatic hypotension with mean systolic blood pressure <90 mmHg at screening or at randomization
12. Any primary cause of HF scheduled for surgery, e.g. valve disease such as severe aortic stenosis or severe mitral regurgitation by the time of screening or randomization
13. History of peripartum cardiomyopathy, chemotherapy induced cardiomyopathy, viral myocarditis, right heart failure in absence of left-sided structural disease, pericardial constriction, genetic hypertrophic cardiomyopathy, or infiltrative cardiomyopathy including amyloidosis

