#### 9.4.2 Safety Analyses

All safety analyses will be performed on the SAF.

The following safety procedures and variables will be assessed during the study:

- SAEs and AEs leading to discontinuation of treatment with study intervention
- Change in body weight from baseline
- Change in serum potassium from baseline
- Number of participants with hyperkalemia (serum potassium  $\geq 5.5$  mmol/L)
- Number of participants with severe hyperkalemia (serum potassium  $\geq 6.0$  mmol/L)
- Number of participants with hospitalization for hyperkalemia
- Number of participants permanently discontinuing study intervention due to hyperkalemia
- Change in vital signs (heart rate, SBP and DBP) from baseline
- Change in renal function measured by eGFR (CKD-EPI formula) change from baseline
- Number of participants with hospitalization for worsening of renal function
- Number of participants permanently discontinuing study intervention due to worsening of renal function
- Changes in laboratory values from baseline.

An overall summary of all AEs and treatment emergent AEs (TEAEs) will be generated by treatment group.

The number and percentage of patients with TEAEs, post-treatment AEs occurring more than 3 days after last intake of study intervention, treatment-emergent SAEs, treatment-emergent study intervention-related AEs, treatment-emergent study intervention-related SAEs, TEAEs causing premature and permanent discontinuation of study intervention, treatment-emergent non-serious AEs, TEAEs by maximum intensity, drug-related TEAEs by maximum intensity will be summarized by treatment group using MedDRA terms grouped by Primary System Organ Class and Preferred Term.

The number of patients with treatment-emergent (until 3 days after last study intervention administration) abnormal laboratory values above or below the normal range will be tabulated by the laboratory parameter and treatment group.

Summary statistics including changes from baseline will be calculated by treatment group and visit for all quantitative laboratory parameters, i.e. for hematology, clinical chemistry and urinalysis. Geometric statistics and ratios to baseline will be presented for urinary albumin-to-creatinine ratio (UACR), creatinine, and NT-proBNP, instead of arithmetic statistics with changes from baseline. For eGFR the relative change will be displayed in addition to the absolute change from baseline.

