4.3 Handling of Missing Data

All missing or partial data will be presented in the subject data listing as they are recorded on the eCRF.

General Rules

When appropriate, the following rules will be implemented so as not to exclude participants or observations from statistical analyses due to missing or incomplete data.

Concomitant medications with missing start and stop date but flagged as being ongoing at a participant’s final visit will be considered to have started prior to study medication start and ended after stopping of study medication. The start and end reference period will be imputed as “before” for the medication start and as “during/after” for the medication end.

In case of partially missing dates for interruptions or permanent stop of study medication intake, a ‘worst-case’ approach will be applied to impute the start and end dates of study medication intake as the earliest and latest possible dates, i.e.:

- first month of the year and/or first day of the month for a partially missing start date, and
- last month of the year and/or last day of the month for a partially missing end date.

If a participant died earlier than the imputed worst study medication end date, the death date will be taken as the study medication end date. However, if these imputations lead to a temporal overlap between different exposure date records, the imputed dates will be adjusted so that no overlap exists and the time on the higher dose is maximized. The date of first exposure to treatment is not expected to be missing as the patients are instructed by the investigator to take their first dose of study drug directly at Visit 1, but in the very rare case

that this date is not recorded, it will be imputed according to the rules outlined above for missing start dates, but not earlier than the randomization date.

When only partial dates are available for clinical events in the efficacy analysis, a median imputation rule will be used:

- For example if the day is missing and the month is July, then day 16 is chosen.
- If the number of potential values is even, the lower of the 2 middle numbers is taken. For example, if the day is missing and the month is June, then day 15 is imputed. The same rule applies if the day and month are missing, e.g. if the year is 2017 and the day and month are missing, 2nd July is used.

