4.5.5 Other Data Handling

Only the data provided by the central laboratory will be used for analysis; values from local laboratories will not be used in the statistical analysis unless otherwise specified and will be listed only. For example, as described above, local values will be used in the derivation of baseline, if no central measurement is available (cf. Section 4.5.1).

At all visits post-randomization and if not stated otherwise, only the values at scheduled measurements will be used for analysis.

For the derived visit “Any time post baseline” (applicable for efficacy) this will include any measurement after randomization, including unscheduled assessments. For the derived visit

“Any time on treatment” (applicable for efficacy), only assessments on or after study medication start date until 30 days after last study drug administration, including unscheduled assessments, will be considered. For safety, “Any time treatment-emergent” will include measurements on or after study medication start date until 3 days after last study drug administration, including unscheduled assessments.

For values which are < LLOQ (Lower limit of quantification), half the value of the LLOQ will be used for analysis. Differences between two values < LLOQ will be assigned values of 0. Ratios between two values < LLOQ will be assigned a value of 1. For values which are > ULOQ (Upper limit of quantification), the ULOQ will be used for analysis.

In case of non-normally distributed data, descriptive statistics other than minimum, maximum and median will only be calculated if at least 2/3 of the individual data were measured and were above the lower limit of quantification. In tables showing descriptive statistics, where values below LLOQ are included, these descriptive statistics will be marked.

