6.4.2 Laboratory Parameters

Generally, only central laboratory measurements will be used for analyses. The only exception is for hematology, where a few countries have the possibility to use local labs in exceptional circumstances (e.g. logistical challenges due to global pandemic, natural disaster, or regional crisis). These local measurements will also be used for the analysis.

The number of participants with treatment-emergent (after the first dose of study drug and up to 3 days after last dose of study drug) abnormal laboratory values above or below the normal range will be tabulated by the laboratory parameter and treatment group.

Summary statistics including changes to baseline will be calculated by treatment group and visit for all quantitative laboratory parameters, e.g. for hematology, NT-proBNP, high sensitive troponin T (hs-TNT), clinical chemistry and urinalysis. Geometric statistics and ratios to baseline will be presented for urinary creatinine, albumin and UACR and NT-proBNP instead of arithmetic statistics with changes from baseline. For eGFR the relative change will be displayed in addition to the absolute change from baseline. Graphical displays will be provided for change from baseline and ratio to baseline by visit, respectively.

Proportion of patients with available and missing measurements will also be displayed.

Summary statistics for serum potassium, eGFR, NT-proBNP and serum creatinine will also be repeated by treatment group and visit separately for each level of the stratification factors.

The following special safety parameters will be further assessed by displaying the number of participants with safety events as described below by treatment group, visit and for any time treatment-emergent (including unscheduled assessments) and up to 3 days after last study drug administration. This will also be performed by stratification factors. The summaries will be performed for the number of participants with:

- Absolute value of serum potassium >5.0 mmol/L, >5.5 mmol/L (hyperkalemia), >6.0 mmol/L (severe hyperkalemia) and >7.0 mmol/L
- Relative decrease from baseline in eGFR of $\geq 25\%$, $\geq 30\%$, $\geq 40\%$, $\geq 50\%$ and $\geq 57\%$, also sustained decrease over 4 weeks
- Absolute value of eGFR < 30 ml/min/1.73m²
- Increase from baseline in serum creatinine >0.3 mg/dL and >0.5 mg/dL.

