The percentage of participants with the respective events (non-stratified) at any time post-baseline (including unscheduled assessments) and within 3 days after last study drug administration will be compared between the finerenone and placebo group by applying separate explorative χ^2 tests with continuity correction. If the expected number of participants in at least 1 cell of the 2x2 contingency table is <5 (Agresti 2005), Fisher's exact test will be applied instead of the χ^2 test. Estimates and two-sided 95% CIs will be provided for each treatment group and the treatment differences. Clopper-Pearson CIs will be calculated for each treatment group, while for treatment differences the exact unconditional confidence limits will be calculated.

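### Treatment-emergent counts for eGFR below 30 and for out-of-range laboratory values ignore the baseline value, so participants already beyond the limit at entry dilute the comparison between arms

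*SAP*

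**What the plan says.** SAP 6.4.2 counts participants with "treatment-emergent (after the first dose of study drug and up to 3 days after last dose of study drug) abnormal laboratory values" and says that "abnormal laboratory values above or below the normal range will be tabulated by the laboratory parameter and treatment group". Protocol 9.4.2 has the same count: "treatment-emergent (until 3 days after last study intervention administration) abnormal laboratory values above or below the normal range". Both definitions concern timing only.

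SAP 6.4.2 then lists special safety parameters to be displayed for any time treatment-emergent, among them an absolute eGFR below 30 mL/min/1.73 m². SAP 4.5.5 defines that derived visit by dates: it "will include measurements on or after study medication start date until 3 days after last study drug administration", unscheduled assessments included. The arms are compared on these parameters as follows: "The percentage of participants with the respective events (non-stratified) at any time post-baseline (including unscheduled assessments") and within 3 days of the last dose, using exploratory chi-square tests with continuity correction (Fisher's exact test if expected counts are small) and confidence intervals for each arm and for the difference.

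The renal exclusion in protocol 5.2 is "eGFR <25 mL/min/1.73 m"², so 25 to below 30 is eligible.

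Neither document requires a baseline inside the limit, requires worsening, restricts the denominator, or plans a laboratory shift table. By contrast, SAP 6.4.1 calls an adverse event treatment-emergent only if it began or got worse on drug, and the eGFR-decrease and creatinine-increase counts in SAP 6.4.2 are measured from baseline.

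**The concern.** A count labelled treatment-emergent should show what happened after treatment began. Here a participant who enters with eGFR 27 and stays at 27 is listed as a safety event. A participant with an analyte already outside its normal range at entry is likewise listed as a treatment-emergent abnormality if it stays there.

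Such cases say nothing about new onset. They raise the percentage in both arms, shrink the difference, move the ratio towards 1 and add noise to the test. In a safety table, attenuation is the unhelpful direction, because it can hide a real excess. SAP 6.4.1 names worsening of renal function as an event of special safety interest, so the number who newly fall below 30 is a natural question that the plan does not answer directly.

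**Working it through.** The documents give no rate, power or sample size for these counts, so there is no planned figure to reproduce. The check is an illustration.

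**Inputs**
- From SAP Section 3: about 6000 randomized 1:1, taken as 3000 per arm.
- Assumed: share f with baseline eGFR below 30 of 3%, 5% or 8%; new onset below 30 among the rest of 9% on finerenone and 7% on placebo (risk ratio 9/7 = 1.29, difference 2.0 points); every participant already below 30 has at least one value below 30 on drug.

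**Formulas**
- Percentage counted in an arm = f + (1 − f) × p.
- Difference counted = (1 − f) × (9% − 7%).
- z = difference / √[(p₁(1 − p₁) + p₂(1 − p₂))/n]; power = Φ(z − 1.96). As written, n = 3000 with the counted percentages. For the at-risk version, n = 3000 × (1 − f) with 9% and 7%.

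**Example, f = 5%**
- Finerenone: 0.05 + 0.95 × 0.09 = 13.55%. Placebo: 0.05 + 0.95 × 0.07 = 11.65%.
- Difference 1.90 points; ratio 1.16.
- z = 0.0190/0.00857 = 2.22, power 60%.
- At risk, n = 2850: z = 0.0200/0.00718 = 2.78, power about 79%.

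| f | Counted, finerenone vs placebo | Difference (points) | Risk ratio | z, power as written | z, power at risk |
|---|---|---|---|---|---|
| 3% | 11.7% vs 9.8% | 1.94 | 1.20 | 2.43, 68% | 2.81, 80% |
| 5% | 13.6% vs 11.7% | 1.90 | 1.16 | 2.22, 60% | 2.78, 79% |
| 8% | 16.3% vs 14.4% | 1.84 | 1.13 | 1.98, 51% | 2.74, 78% |

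**Sensitivity**
- With the planned continuity correction (subtract 1/n from the difference), power is 66%, 59% and 49% as written, against 79%, 78% and 77% at risk.
- If only 90% of those already below 30 have such a value on drug, the ratios are 1.20, 1.17 and 1.13.
- Other assumptions (8% vs 10% new onset, 95% persistence) give the same pattern: the ratio falls from 1.25 to 1.20, 1.15 and 1.11 at f = 2%, 5% and 10%.

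**Normal-range table.** If 20% are abnormal at entry and new onset is 13% vs 10%, the table shows 0.20 + 0.80 × 0.13 = 30.4% against 0.20 + 0.80 × 0.10 = 28.0%. No test is planned there, so the dilution is descriptive.

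**Window wording.** Protocol 1.3 says "All procedures at Visit 1 are to be performed prior to randomization", and SAP 4.3 says "the patients are instructed by the investigator to take their first dose of study drug directly at Visit 1". The Visit 1 sample and the first dose can therefore share a date. Under the date rule in SAP 4.5.5, that pre-dose sample falls inside the treatment-emergent window. Two parts of SAP 6.4.2 exclude it: the normal-range count starts after the first dose, and the test is worded as post-baseline. The overlap touches only the special-parameter displays that rely on the 4.5.5 rule.

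**The case against.** The strongest reply is that little depends on these counts. The tests are exploratory and no power was claimed for them. The plan reports differences, not risk ratios, and on these assumptions the difference moves by no more than 0.16 points. The power loss rests on prevalence and incidence figures that are not in the documents. The renal package is also broad: eGFR decreases at five cut-offs (also sustained), creatinine rises, changes from baseline by visit, and renal adverse events, hospitalizations and discontinuations. The standard tables cited in SAP 4.1 might contain a baseline rule. All of this stands and holds the severity down. It does not supply the missing rule: neither document shows one, and the decrease counts do not say how many newly fell below 30.

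A reader might infer more than the documents support:
- **That potassium counts are equally affected.** Protocol 5.2 excludes potassium above 5.0 mmol/L at screening or randomization, so the counts above 5.5, 6.0 and 7.0 are hardly touched. Only the count above 5.0 is exposed, where the local entry value and the central analysis value disagree.
- **That the baseline sample enters every treatment-emergent count.** SAP 6.4.2 rules this out for the normal-range counts and for the tests.
- **That the normal-range tables give a biased test.** They are tabulated only.
- **That raised creatinine at entry must be very common because eGFR 60 divides the population.** That value sets the dosing group; the documents give no share on either side.

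**Conclusion.** The point holds for two counts, eGFR below 30 and values outside the normal range. Read as written, both include participants already beyond the limit at entry, and the first feeds an exploratory test. The consequence is attenuation, not false imbalance, because randomization balances these participants between arms.

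The size is conditional on the assumed baseline share and new-onset rates, and on most participants who start below 30 staying there. The difference barely moves; the ratio and the power of the test move more. It would be wrong to conclude that the renal safety objective goes unanswered or that efficacy inference is at risk: the baseline-referenced counts partly compensate, and no confirmatory test uses these data. This is a cheap improvement of low severity.

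**What to change.** 1. In SAP 6.4.2, for eGFR below 30 and the normal-range counts, count an event only in participants whose baseline is not already beyond that limit in the same direction and who have at least one post-baseline value. Use that number as the denominator for the percentages and, for eGFR below 30, for the test and confidence intervals.
2. Add a baseline-to-worst shift table, so that participants already beyond the limit, including those with the lowest eGFR, stay visible.
3. Align the window in SAP 4.5.5 with the after-first-dose wording in SAP 6.4.2, so that the pre-dose Visit 1 sample is excluded.
4. Carry the same wording into protocol 9.4.2. If the standard tables already hold such a rule, state it in the SAP.

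The cost is wording, a denominator filter and one table; no new data are needed. The downside is a slightly smaller denominator, and the participants with the lowest eGFR leave the tested comparison for eGFR below 30, which is why the shift table belongs with the change.
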